 - The participants will be randomized to dupilumab or placebo in 1:1 ratio with stratification factors of documented history of atopy (atopic or non-atopic), stable use of TCS/TCI (yes or no), and country/territory code. Number of participants with active mild AD upon study entry will represent up to 10% of the atopic participants. Both the atopic and the non-atopic PN population will be capped at 60% of the total enrolled population.
- **Sample size calculation**
 - The primary endpoint is the proportion of participants with a WI-NRS reduction of ≥ 4 from baseline to Week 24. Assuming a response rate of [] and [] in placebo and dupilumab respectively, 56 participants/arm will provide 90% power to detect the difference of [] between dupilumab and placebo with Fisher exact test at 2-sided level of 0.05. Assuming 15% drop out during treatment, the target is to randomize 75 participants/arm to allow for up to 10% of atopic patients having active mild AD upon study entry.
- **Primary analysis**
 - The analysis population for the efficacy endpoints will be the intent-to-treat (ITT) population defined as all randomized participants analyzed according to the treatment group allocated by randomization regardless if treatment kit is used or not.
- **Analysis of primary endpoint**
 - The primary analysis on WI-NRS reduction ≥ 4 at Week 24 will be conducted by using Cochran-Mantel-Haenszel (CMH) test stratifying by stratification factors (documented history of atopy [atopic or non-atopic], stable use of TCS/TCI [yes or no], and region [countries combined]) and covariate of baseline anti-depressant use (yes or no). For participants discontinuing the study treatment before Week 24, their off-study treatment values measured up to Week 24 will be included in the analysis. Participants taking selected prohibited medications and/or rescue medications (details of selection will be specified in the statistical analysis plan [SAP]) prior to Week 24 or have missing data at Week 24 will be considered non-responders.
 - Sensitivity analyses using alternative methods will be performed to handle missing data and/or data collected after participants taking selected prohibited medications and/or rescue medications. A subgroup analysis will be performed excluding participants with a current diagnosis of AD. More details of the sensitivity and subgroup analyses will be specified in the SAP.
- **Analysis of secondary endpoints**

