6.5 CONCOMITANT THERAPY

Any medication or vaccine (including over-the-counter or prescription medicines, vitamins, and/or herbal supplements) that the participant is receiving at the time of enrollment or receives during the study must be recorded along with:

- Reason for use.
- Dates of administration including start and end dates.
- Dosage information including dose and frequency.

The concomitant use of non-sedating antihistamine administration is allowed during the study except for treatment of AD or PN, but dose change of non-sedating antihistamine is not allowed both from Week 11 to Week 12 and from Week 23 to Week 24.

The concomitant use of the following therapies is prohibited during the entire study. Study treatment will need to be discontinued in participants receiving these treatments:

- Systemic immunosuppressive/immunomodulating drugs (eg, systemic corticosteroids, cyclosporine, mycophenolate-mofetil, interferon gamma, Janus kinase inhibitors, azathioprine, methotrexate, hydroxychloroquine, dapsone, sulfasalazine, colchicine, etc).
- Other monoclonal antibodies (which are biological modifiers).
- Phototherapy, including tanning beds.
- Naltrexone or other opioid antagonist.
- Gabapentin, pregabalin, and thalidomide.

The concomitant use of the following therapies is prohibited except if the dose has been stable for at least 3 months prior to screening, but study treatment will not need to be discontinued in participants receiving the treatments listed below. The dose should also remain stable (can be reduced or discontinued if medically indicated), but should not be initiated or increased throughout the study.

- Paroxetine, fluvoxamine, or other SSRIs.
- SNRIs.
- Amitriptyline or other tricyclic or tetracyclic antidepressants.

The concomitant use of the following therapies is also prohibited during the entire study, but study treatment will not need to be discontinued in participants receiving the treatments listed below.

- Intralesional corticosteroid injections and cryotherapy.
- Sedating antihistamine.
- Non-sedating antihistamine used specifically for the treatment of itch secondary to AD or PN.

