9.4.1 Efficacy analyses

The multiplicity procedure is proposed to control the overall Type-I error rate for testing the primary endpoint and the key secondary endpoints. Detailed hierarchical testing procedure will be defined in the study SAP. The study is considered positive when the primary endpoint achieves statistical significance with two-sided significance level of 0.05.

The analysis population for the efficacy endpoints will be the ITT population.

Modification in accordance with the above proposal will be documented in the SAP prior to the database lock.

Table 6 - Efficacy analyses

Endpoint	Statistical analysis methods
Primary: Proportion of participants with improvement (reduction) in WI-NRS by ≥ 4 from baseline to Week 24	
The primary analysis will be conducted by using CMH test stratifying by stratification factors (documented history of atopy [atopic or non-atopic], stable use of TCS/TCI [yes or no], and region [countries combined]) and covariate of baseline anti-depressant use (yes or no).
 
For participants discontinuing the study treatment before Week 24, their off-study treatment values measured up to Week 24 will be included in the analysis. Participants taking selected prohibited medications and/or rescue medications (details of selection will be provided in the SAP) prior to Week 24 or have missing data at Week 24 will be considered non-responders.
 
Sensitivity analyses:
 
The data collected after taking selected prohibited medications and/or rescue medications will not be censored and included in the sensitivity analysis to evaluate the robustness of the primary analysis results with respect to the method of handling data while taking selected prohibited medications. Details of the sensitivity analyses will be provided in the SAP.
 
Subgroup analyses:
 
To assess the consistency in treatment effects across different subgroup levels, subgroup analyses will be performed for the primary efficacy endpoint with respect to documented history of atopy (atopic or non-atopic), age group, gender, region, and other factors that will be specified in the SAP. A subgroup analysis will be performed excluding participants with a current diagnosis of AD.

Key secondary: Proportion of participants with IGA PN-S 0 or 1 score at Week 24.	The key secondary efficacy endpoint that measures binary responses will be analyzed in the same fashion as the primary endpoint.

Endpoint	Statistical analysis methods

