1.2.1 Estimands

The primary estimands defined for main endpoints are summarized in below [Table 3](#). More details are provided in [Section 4](#).

Table 3 - Summary of primary estimand for main endpoints

Endpoint Category	Estimands			
	Endpoint(s) ^a	Population	Intercurrent event(s) strategy and missing data handling	Population-level summary
Primary objective: To demonstrate the efficacy of dupilumab on itch response in participants with PN, inadequately controlled on topical prescription therapies or when those therapies are not advisable.				
Primary endpoint	Proportion of participants with improvement (reduction) in worst-itch numeric rating scale (WI NRS) by ≥ 4 from baseline to Week 24	ITT	
The intercurrent events will be handled as follows:
 
 Discontinuation of study treatment before Week 24: Off-study treatment data up to Week 24 will be included in the analysis (treatment policy strategy). Taking the prohibited medications/procedures and/or rescue medications^b prior to Week 24: Participants will be considered as non-responders (composite strategy). 
In addition, the missing data imputation rules are as follows:
 
 Having missing data at Week 24: Participants will be considered as non-responders 	CMH test adjusted by documented history of atopy (atopic or non-atopic), stable use of TCS/TCI (yes or no), region (countries combined), and baseline antidepressant use (yes or no).
Secondary objective: To demonstrate the efficacy of dupilumab on additional itch endpoints in participants with PN, inadequately controlled on topical prescription therapies or when those therapies are not advisable.				

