4.3 PRIMARY ENDPOINT(S) ANALYSIS

4.3.1 Definition of endpoint(s)

The primary endpoint for this study is the proportion of participants with improvement (reduction) in worst-itch numeric rating scale (WI-NRS) by ≥ 4 from baseline to Week 24.

WI-NRS is a patient-reported outcome (PRO) comprised of a single item rated on a scale from 0 (“No itch”) to 10 (“Worst imaginable itch”). Participants are asked to rate the intensity of their worst pruritus (itch) over the past 24 hours using this scale.

The weekly average WI-NRS score at each week, which is defined as the average of daily non-missing scores within the week window of each week (see [Section 5.4](#)), will be used for analyses.

For efficacy analysis, [Table 5](#) presents the prohibited and rescue medications/procedures which will be considered as intercurrent events if the last column indicates as “Yes” and therefore be handled in the estimands for endpoints defined in [Table 3](#).

Table 5 - Prohibited medications/procedures and rescue medications that impact efficacy

Medication/procedure	Comment	Data to be set as non-responder after taking medication in the main statistical analysis (Yes/No) ^a /Selection criteria
Prohibited medications/procedures		
Systemic immunosuppressive/immunomodulating drugs (eg, systemic corticosteroids, cyclosporine, mycophenolate-mofetil, interferon gamma, Janus kinase inhibitors, azathioprine, methotrexate, hydroxychloroquine, dapsone, sulfasalazine, colchicine, etc)	IMP to be discontinued	Yes (CDG ^b Immunosuppressant drugs Narrow and SDG ^b Corticosteroids Narrow)
Other monoclonal antibodies (that are biological response modifiers).	IMP to be discontinued	Yes (SDG ^b SDGMonoclonal antibodies Narrow)
Phototherapy, including tanning beds.	IMP to be discontinued	Yes (CMQ ^b HLT Phototherapies, CMQ ^b Tanning_single PT)
Naltrexone or other opioid antagonist	IMP to be discontinued	Yes (SDG ^b Analgesia producing opioids NARROW)
Gabapentin, pregabalin, and thalidomide	IMP to be discontinued	Yes (CDG ^b Gabapentin mono and multi ingredients, Pregabalin mono and multi ingredients, or Thalidomide mono and multi ingredients)
Paroxetine, fluvoxamine or other SSRIs.	No IMP discontinuation, see requirement in the footnote	Yes ^{c,d} (CDG ^b N06AB selective serotonin reuptake inhibitors)
SNRIs.	No IMP discontinuation, see requirement in the footnote	Yes ^{c,d} (CDG ^b serotonin and norepinephrine reuptake inhibitors)

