Amitriptyline or other tricyclic or tetracyclic antidepressants	No IMP discontinuation, see requirement in the footnote	Yes ^{c,d} (CDG ^b N06AA non-selective monoamine reuptake inhibitors)
Intralesional corticosteroid injections and cryotherapy.	No IMP discontinuation	Yes ^d (CMQ ^b Injection_single pt, cryotherapy or skin cryotherapy PT)
Sedating antihistamine	No IMP discontinuation	Yes ^{d,e} (CDG ^b sedating antihistamines)
Non-sedating antihistamine if used specifically for the treatment of itch secondary to AD or PN	No IMP discontinuation	Yes ^{d,e} (CDG ^b non-sedating antihistamines)

Medication/procedure	Comment	Data to be set as non-responder after taking medication in the main statistical analysis (Yes/No) ^a /Selection criteria
Rescue medications		
Dermatological preparations of high potency or superpotent TCS and TCI	No IMP discontinuation	Yes ^d (CDG ^b calcineurin inhibitors and corticosteroids narrow, Ticked 'RESCUE THERAPY' in CRF page)
a When yes, the estimand for the intercurrent event handling strategy will be as follows: hypothetical for continuous endpoints, and composite for responder and time-to-event endpoints. When no, a treatment policy strategy will be applied. b CDG=company drug groupings, CMQ=company MedDRA query, SDG= Standardized drug groupings. c Only if the antidepressant is initiated during the study or its dose is increased from baseline provided that medication was taken at least 3 months prior to screening. d As per medical adjudication, see Section 5.7 for details. e Only if the medication is initiated at Week 12 or Week 24, or the dose is increased from Week 11 to Week 12 or from Week 23 to Week 24.		

Blinded review of prohibited/rescue treatment (medication or procedure) based on [Table 5](#) and a pre-specified algorithm ([Section 5.7](#)) will be implemented before database locks by considering the type of medication or procedure, indication, timing, frequency and the potential impact of the use of the prohibited medications/procedures and rescue medications.

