4.3.2 Main analytical approach

The primary estimand for the primary endpoint is the treatment policy/composite approach as defined in [Table 3](#).

The primary analysis population for the efficacy endpoints will be the ITT population.

The following null hypothesis H0 and alternative hypothesis H1 will be tested for dupilumab against placebo:

- H0: No treatment difference between dupilumab and placebo.
- H1: There is a treatment difference between dupilumab and placebo

The primary analysis will be conducted by using Cochran–Mantel–Haenszel test (CMH) test adjusted by documented history of atopy (atopic or non-atopic), stable use of TCS/TCI (yes or no), region, and baseline anti-depressant use (yes or no). Comparisons of the response rates between dupilumab and placebo will be derived. In addition, odds ratio and response rate difference as well as the corresponding 95% confidence intervals (CI) will be provided along with the p-values.

As defined in [Table 3](#) for participants discontinuing the study treatment before Week 24, their off-study treatment values measured up to Week 24 will be included in the analysis. Participants taking the prohibited medications/procedures and/or rescue medications (see [Table 5](#)) prior to Week 24 or having missing data at Week 24 will be considered non-responders.

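### Footnote e of SAP Table 5 leaves prohibited antihistamine use started outside Weeks 12 and 24, and continued at constant dose through Week 24, without a pre-specified non-response rule

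*SAP*

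**What the plan says.** SAP 4.3.1 introduces Table 5 as the list of medications and procedures "which will be considered as intercurrent events if the last column indicates as" Yes. Two antihistamine rows are marked Yes: sedating antihistamines, and non-sedating antihistamines used for itch secondary to AD or PN. Both carry footnotes d and e. Footnote d sends the case to medical adjudication under 5.7. Footnote e restricts the event: "Only if the medication is initiated at Week 12 or Week 24, or the dose is increased from Week 11 to Week 12", and it goes on to add an increase from Week 23 to Week 24.

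Protocol 6.5 puts both categories, together with intralesional corticosteroid injections and cryotherapy, in a list headed "The concomitant use of the following therapies is also prohibited during the entire study". In a different sentence, on permitted non-sedating antihistamines, it says that "dose change of non-sedating antihistamine is not allowed both from Week 11 to Week 12 and from Week 23 to Week 24".

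For the primary endpoint, SAP 4.3.2 says that participants taking these medications "prior to Week 24 or having missing data at Week 24 will be considered non-responders". Table 3 has the same rule under a composite strategy: "prior to Week 24: Participants will be considered as non-responders (composite strategy". The protocol leaves the choice of medications to the SAP. Its 9.4.1 speaks of "Participants taking selected prohibited medications and/or rescue medications (details of selection will be provided in the SAP) prior to Week 24", and the Synopsis says the same.

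The SAP version history (version 3.0) explains why the word *selected* was removed: taking any prohibited medication named in the protocol makes a participant a non-responder once blinded adjudication has confirmed it.

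**The concern.** The primary endpoint compares the Week 24 weekly mean itch score with baseline. A prohibited anti-itch drug started after baseline and still being taken in that week can affect every daily score in the mean. Footnote e does not ask about that. It asks whether the drug was started, or its dose raised, near one of two assessment weeks. That test suits a permitted drug already stable at baseline, which is how Protocol 6.5 uses the Week 11–12 and Week 23–24 intervals. It does not suit a drug that should not be taken at all.

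The flag decides who is a non-responder on the primary endpoint. SAP 4.4.1.2 applies the same estimand to the key secondary endpoints, and Table 5 footnote a carries the flag to the continuous and time-to-event endpoints. No supplementary analysis in 4.3.4 uses a wider event definition. The as-observed analysis ignores these events altogether, and the hybrid and tipping-point analyses give no other definition of them.

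**Working it through.** The plan states no figure on this point, so there is none to reproduce. The check compares the texts and then counts start days.

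**Inputs.** SAP 5.4, Table 10 (weekly windows for the itch diary): Week 11 = Days 75–81, Week 12 = Days 82–88, Week 23 = Days 159–165, Week 24 = Days 166–172. Protocol 9.2: about 75 participants per arm. Footnote e does not define *at Week 12* or *at Week 24*; taking them as the Table 10 windows is an assumption.

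**Three constant-dose cases under the literal text**

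| Start of drug | Meets footnote e? | Before Week 24 (Table 3, 4.3.2)? | Week 24 daily scores at or after start |
|---|---|---|---|
| Week 16, continued | No | Yes | 7 of 7 |
| Week 12, stopped well before Day 166 | Yes | Yes | none while on drug |
| Day 172 | Yes | Hardly | at most 172 − 172 + 1 = 1 of 7 |

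The only start that clearly meets both footnote e and the before-Week-24 condition is one at Week 12. Every Yes in the second column is still subject to adjudication under footnote d.

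**Start days outside footnote e, Days 1–172**
- Inside: 7 (Week 12) + 7 (Week 24) = 14.
- Outside: 172 − 14 = 158, or 158/172 = 91.9%. These are Days 1–81 (81 days) and Days 89–165 (165 − 89 + 1 = 77 days); 81 + 77 = 158.
- Before the Week 24 window (Days 1–165): 165 − 7 = 158 outside, or 158/165 = 95.8%.
- Looser reading, in which going from no drug to drug is a dose increase, so that Week 11 and Week 23 starts also qualify: 158 − 7 − 7 = 144 outside, or 144/172 = 83.7%.
- Narrower reading, target days only (Days 85 and 169): 169 − 2 = 167 of 169 outside.

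These are counts of calendar days, not of participants. They show how little of the treatment period the criterion covers under any reading, not how often it would matter.

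**Effect of one participant.** 1/75 = 1.33 percentage points on that arm's response rate. The documents give no antihistamine-use rate and the assumed response rates are redacted, so no effect on power or bias can be derived.

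**Comparison within Table 5.** Intralesional corticosteroids and cryotherapy, from the same Protocol 6.5 list, carry footnote d with no time window. Footnote c counts an antidepressant started at any time during the study. The SAP gives no reason for treating antihistamines differently.

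**The case against.** **The protocol delegates the selection to the SAP.** This stands. A reader might infer that footnote e simply contradicts the protocol. It does not: a medication can be prohibited and still not be selected as an intercurrent event. The difficulty is that this selection is unexplained and fits poorly with Table 3, 4.3.2 and the sponsor's stated intent in the version history.

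**Adjudication may catch these cases.** This stands in part. Under 5.7 item 2, antihistamine use for PN-consistent indications goes to blinded review whenever it began, and reviewers weigh timing, frequency, dose and likely impact. A reader might infer that someone starting at Week 16 will certainly pass as a responder; the documents do not support that. But reviewers are told to apply the Table 5 criteria as well, and nothing says that the other considerations outrank *only if*. The broader review in footnote 1 of 5.7 is optional and attached to item 1, where antihistamines are not listed. The review in Protocol 6.5.1 concerns rescue treatment.

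**A start at Week 24 does not simply count.** Correct. It meets footnote e, but it is hardly before Week 24 and it needs adjudication. The contrast with a mid-period start shows an inconsistency in the criterion, not a known difference in final classification.

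**Antihistamines may do little in PN.** Protocol 2.2 describes weak evidence for them. That is a plausible reason for a lenient rule, but the SAP does not give it, and it would not explain why starts at Weeks 12 and 24 are the ones that count.

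**Use will be visible.** SAP 5.3 reports the number taking prohibited medications and the time to first use, so an imbalance could be seen. No responder analysis reclassifies those participants.

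**Conclusion.** The point holds as a defect in the pre-specified event definition. Read literally, footnote e excludes post-baseline use of two prohibited antihistamine categories that began before Week 12, or between the Week 12 and Week 24 windows, and continued at constant dose through the Week 24 assessment. Table 3 and 4.3.2 count use before Week 24, and the version 3.0 rationale points the same way. That rationale is a change-log entry, so it is evidence of intent; the point does not depend on it. Whether adjudication would still capture such use is left open.

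Between 144 and 158 of 172 start days fall outside the criterion under the two window-based readings, and 167 of 169 under the target-day reading. The weight on the result is 1.33 points per arm for each participant classified differently, at 75 per arm. A reader might infer bias in favour of dupilumab. The documents do not support that: frequency is unknown, and if uncounted use were commoner on placebo and reduced itch, it would raise the placebo response and work against dupilumab. The footnote should be corrected before unblinding; nothing here shows that the trial's conclusion would change.

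**What to change.** Before unblinding, reconcile footnote e with Protocol 6.5, SAP Table 3, 4.3.2, the version 3.0 rationale and 5.7. For the analysis definition, remove the time window from the two antihistamine rows and keep footnote d. Post-baseline use before the analysis timepoint, including use that continues into the analysis week, then goes to blinded adjudication.

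If the sponsor keeps footnote e, the SAP should give the reason, define *at Week 12* and *at Week 24*, and say whether the footnote or the adjudicators' judgement governs. It should also add one supplementary analysis of the primary and key secondary endpoints in which adjudicated use of either category at any time before Week 24 is non-response.

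The cost is one footnote or one extra analysis, a slightly longer adjudication listing, and possibly a few more non-responders. Removing the window also gives adjudicators somewhat more room for judgement in place of a fixed criterion. This concerns the analysis definition only; no clinical rule is proposed.

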4.3.2 Main analytical approach

The primary estimand for the primary endpoint is the treatment policy/composite approach as defined in [Table 3](#).

The primary analysis population for the efficacy endpoints will be the ITT population.

The following null hypothesis H0 and alternative hypothesis H1 will be tested for dupilumab against placebo:

- H0: No treatment difference between dupilumab and placebo.
- H1: There is a treatment difference between dupilumab and placebo

The primary analysis will be conducted by using Cochran–Mantel–Haenszel test (CMH) test adjusted by documented history of atopy (atopic or non-atopic), stable use of TCS/TCI (yes or no), region, and baseline anti-depressant use (yes or no). Comparisons of the response rates between dupilumab and placebo will be derived. In addition, odds ratio and response rate difference as well as the corresponding 95% confidence intervals (CI) will be provided along with the p-values.

As defined in [Table 3](#) for participants discontinuing the study treatment before Week 24, their off-study treatment values measured up to Week 24 will be included in the analysis. Participants taking the prohibited medications/procedures and/or rescue medications (see [Table 5](#)) prior to Week 24 or having missing data at Week 24 will be considered non-responders.

